6.5.3.1 Subgroup Analysis

Subgroup analysis on PFS will be performed on FAS as well as Tumor Response Evaluable Set using the subgroups defined for the CBR subgroup analysis.

6.5.4 Duration of Response

Duration of Response (DOR) is a secondary endpoint for all cohorts. It is defined as the time (in months) from the date of first documented response (that is subsequently confirmed per RECIST version 1.1) until date of documented progression or death in the absence of PD: (date of first radiologic PD or death – date of first response + 1) / 30.4375. The end of response should coincide with the date of progression or death from any cause. The time of initial response will be defined as the latest of the dates contributing to the first visit response of PR or CR.

Subjects who have not progressed following a response at the time of analysis will be censored at the date of last evaluable tumor assessment. Subjects who receive other anticancer therapy prior to documented PD will be censored the day this subsequent therapy started.

DOR will be summarized using Kaplan-Meier methodology² in a tabular format.

The proportion of subjects with a DOR of 6 months or more will be summarized.

Censoring rules used for DOR are the same as the ones for PFS ([Table 3](#)).

If there are a sufficient number of responses (n=10), DOR will be analyzed using the same methodology as PFS.

6.5.5 Overall Survival

Overall Survival (OS) is a secondary endpoint for all cohorts. It is defined as the time from date of first dosing until the date of death. Subjects alive at the time of analysis will be censored at the time of the latest date of survival status assessment.

6.5.6 Pharmacokinetic Variables

Plasma samples for ZN-c5 and its potential metabolites as applicable, and palbociclib (and metabolite) were collected as below. In case the dosing schedule was changed to BID dosing, an additional PK time point at 12 hours post ZN-c5 dosing was drawn (optional).

Day on Study	Time (hr)	Monotherapy	Combination Therapy	
		ZN-c5	ZN-c5	Palbociclib
Cycle 1 Day 1 and 15	T=0	PK (pre-dose, within 0.5 hrs)	PK (pre-dose, within 0.5 hrs)	NA
		Dose (fasted)	Dose (fasted)	NA
	0.5	PK	PK	NA
	1	PK	PK	NA
	2	PK	PK (prior to Palbociclib dosing)	PK (pre-dose, within 0.5 hrs)
				Dose (with food)
	2.5	NA	NA	PK (0.5-hr)
	3	NA	NA	PK (1-hr)
	4	PK	PK	PK (2-hr)
	6	PK	PK	PK (4-hr)
	8	PK	PK	PK (6-hr)
	10	NA	NA	PK (8-hr)
Cycle 1 Day 2 and 16	24	PK	PK	NA
	26	NA	NA	PK (24-hr)
Cycle 1 Day 8		PK (pre-dose, within 0.5 hrs)	PK (pre-dose, within 0.5 hrs)	PK
Cycle 2 Day 1		PK (pre-dose, within 0.5 hrs)	PK (pre-dose, within 0.5 hrs)	NA
Cycle 3 Day 1		PK (pre-dose, within 0.5 hrs)	PK (pre-dose, within 0.5 hrs)	NA
Cycle 4 Day 1		PK (pre-dose, within 0.5 hrs)	PK (pre-dose, within 0.5 hrs)	NA
NA= not applicable				

6.5.7 Pharmacodynamic/Biomarker Analysis

Exploratory analyses may be performed to evaluate the association of each biomarker or combination of biomarkers with clinical outcomes, and the modulation of biomarkers related to mechanism of action and PD.

Exploratory biomarkers analyses that may enhance the understanding of the biological effects, the mechanism of action, or safety, may be performed. Biomarker objectives may be further described and updated based on evolving scientific knowledge of ZN-c5 activity.

If an exploratory biomarker analysis is to be performed, this SAP will be updated with details on objectives and analysis methods, prior to the actual data analysis.

6.6 Safety

All safety analyses will be based on the Safety Analysis Set, except for evaluation of DLTs, which will be based on the DLT-Evaluable Analysis Set.

Safety parameters that will be measured in the study are:

- Adverse events
- Dose-limiting toxicities (DLTs; Monotherapy and Combination Therapy Dose Escalations only)
- Laboratory measurements (hematology, coagulation, serum chemistry, urinalysis)
- Vital signs
- ECG
- Physical examination
- ECOG PS

Safety data will be presented descriptively; no formal statistical analyses will be performed.

6.6.1 Study Day and Visit Window Definitions

Nominal visit assignment as collected on the CRF will be used to analyze safety parameters presented by visit. Any unscheduled assessments will not be included in by-visit summaries but are eligible in “worst case” analyses. ECG data collected in triplicate will be averaged and handled as a single collection for visit assignment.

Study day is defined as the date of assessment – first date of exposure + 1 for assessments that occur on or after the first date of exposure; study day is defined as the date of assessment – fist date of exposure for assessments that occur prior to the first date of exposure. The same methodology will be used to define relative cycle day, where day 1 of a given cycle is defined based on the visit date reported on the Date of Visit eCRF.

6.6.2 Extent of Exposure to Study Medication

The following exposure parameters will be calculated separately for each study drug (ZN-c5, and palbociclib, as applicable), with dates of exposure being defined as dates where any study drug is taken.

The treatment duration will be calculated as last date of exposure – first date of exposure + 1 for ZN-c5, and last date of exposure – first date of exposure + 8 for palbociclib.

The **number of doses prescribed** will be calculated based on the treatment duration of study drug. For ZN-c5, this will be the number of days of study drug for subjects assigned to QD dosing schedule and will be the number of days of study drug * 2 for subjects assigned to BID dosing schedule. For palbociclib, this will be the ceiling (treatment duration of study drug / 28) * 21.

The **number of doses taken/administered** will be calculated as (treatment duration of study drug * planned number of doses per day) – number of missed doses.

The **percent of expected doses taken/administered** will be calculated as [(number of doses taken/administered) / (number of doses prescribed)] * 100%.

The **total exposure** will be calculated (in mg) for each study drug as the sum of doses taken/administered in mg.

The **actual daily dose** for ZN-c5 and palbociclib will be calculated as the total exposure / number of days of study drug.

The **relative dose intensity (RDI)** for ZN-c5 and palbociclib will be calculated as (actual daily dose / planned daily dose) * 100%.

The **occurrence of dose modifications** (Yes, No) will be derived by subject and reason (AE, other) for each type of modification (drug interruption, dose reduced, dose escalated, drug discontinued).

The **number of dose modifications** will be derived by subject for each type of modification.

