8.4.3.2 DOSE ADJUSTMENT OF PALBOCICLIB

For subjects participating in the combination therapy portion of the study with toxicity potentially attributable to palbociclib, please follow safety and toxicity guidelines in the most recent local or US Full Prescribing Information for palbociclib (IBRANCE®, Pfizer Inc.).

Dose holds for reasons other than toxicity (e.g., scheduled surgery) are allowed for up to 21 days. Dose holds for reasons other than toxicity that last more than 21 days require that the subject be removed from study unless deemed in the best interest of the patient to continue and after discussion between the Investigator and the Sponsor's Medical Monitor (Section 7.2).

Unmanageable AEs attributed to palbociclib alone may result in continuation of single agent ZN-c5 therapy as long as none of the treatment discontinuation criteria are met (Section 7.2).

If treatment with ZN-c5 is discontinued, on-study treatment with palbociclib can be continued per protocol unless palbociclib is commercially available and treatment is reimbursed for the patient, then the patient can come off study treatment.

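### SAP 6.6.2 defines exposure dates by any study drug while calculating exposure per drug; taken literally, this inflates duration and doses prescribed in combination subjects

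*SAP*

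**What the plan says.** The opening sentence of SAP 6.6.2 sets the level of calculation as each study drug separately. It then defines the dates that feed the calculation, "with dates of exposure being defined as dates where any study drug is taken". Treatment duration follows as "last date of exposure – first date of exposure + 1 for ZN-c5, and last date of exposure – first date of exposure + 8 for palbociclib".

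Doses prescribed are derived from that duration. ZN-c5 gets one dose per day of study drug on a once-daily schedule and two on a twice-daily schedule. "For palbociclib, this will be the ceiling (treatment duration of study drug / 28) * 21". The percentage of expected doses divides doses taken by doses prescribed. Actual daily dose divides total milligrams by the number of days of study drug, and relative dose intensity (RDI) divides that by the planned daily dose.

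The SAP nowhere gives a first or last date specific to one drug. In SAP 6.6.3, adverse-event summaries for the Phase 1 combination are planned for any study drug and also separately for ZN-c5 and palbociclib, so there the phrase means either drug.

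Protocol 8.4.3.2 allows the two drugs to part company in both directions: "Unmanageable AEs attributed to palbociclib alone may result in continuation of single agent ZN-c5 therapy", provided no discontinuation criterion is met, and "If treatment with ZN-c5 is discontinued, on-study treatment with palbociclib can be continued per protocol", with an exception where palbociclib is commercially available and reimbursed.

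**The concern.** The two halves of one sentence pull against each other. A per-drug duration needs per-drug dates, but the stated dates belong to the regimen. In a monotherapy subject there is no difference. In a combination subject the last date of exposure is the later of the two drugs' last days, and both durations run to it.

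Two consequences follow from the literal text. First, the palbociclib offset adds the 7 rest days after a Day 21 dose, but ZN-c5 is dosed continuously, so the regimen's last day can already lie inside that rest week. Second, when one drug is stopped and the other goes on, the stopped drug keeps accruing duration and prescribed doses. Protocol 9.4.4.1 asks for doses prescribed, percentage of expected doses taken and days of study drug by dose level. These tables help a reader judge tolerability, which is a secondary objective in the combination cohorts.

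**Working it through.** The plan states no numerical result here, so there is no figure to reproduce. The check applies the SAP 6.6.2 formulas twice, with regimen dates as written and with each drug's own dates.

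**Inputs.** Palbociclib 125 mg daily, 21 days on and 7 off in a 28-day cycle (Protocol 6.1.2.2). ZN-c5 continuous (Protocol 6.1.4 and 6.1.5), once daily in these examples. Both start on Day 1 (Schedule of Activities), so only the last date matters. The number of cycles and the stop days are my assumptions.

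**Formulas.** ZN-c5 duration = last − first + 1. Palbociclib duration = last − first + 8. Palbociclib doses prescribed = ceiling(duration / 28) × 21.

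**1. Nothing stopped, one complete cycle** (palbociclib to Day 21, ZN-c5 to Day 28).
- Own dates: 21 − 1 + 8 = 28 days; ceiling(28/28) × 21 = 21 doses.
- As written: 28 − 1 + 8 = 35 days; ceiling(35/28) × 21 = 2 × 21 = 42 doses.

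The extra cycle does not need ZN-c5 to reach Day 28. A last ZN-c5 dose on Day 22 gives 22 − 1 + 8 = 29 days, and the ceiling already rounds up to two cycles. Any final ZN-c5 day from 22 to 28 of a cycle has this effect.

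**2. Nothing stopped, six complete cycles** (palbociclib to Day 5 × 28 + 21 = 161, ZN-c5 to Day 168).
- Own dates: 161 − 1 + 8 = 168 days; 6 × 21 = 126 doses.
- As written: 168 − 1 + 8 = 175 days; ceiling(6.25) × 21 = 147 doses. The 126 doses actually taken are 126/147 = 85.7% of those prescribed, instead of 100%.

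**3. Palbociclib stopped after Day 77, ZN-c5 to Day 168.**
- Own dates: 77 − 1 + 8 = 84 days; 3 × 21 = 63 doses; 63/63 = 100%.
- As written: 175 days; 147 doses; 63/147 = 42.9%.

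**4. ZN-c5 stopped on Day 56, palbociclib to Day 161.**
- Own dates: 56 days and 56 doses prescribed.
- As written: 161 − 1 + 1 = 161 days and 161 doses; 56/161 = 34.8% instead of 100%.

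The percentages count doses actually taken. The SAP's own formula for doses taken also starts from duration and subtracts missed doses, so its result would depend on whether days after stopping, and palbociclib rest days, are recorded as missed. That is a separate ambiguity.

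**Dose intensity, under one further assumption.** SAP 6.6.2 does not define the number of days of study drug. The sentence on ZN-c5 doses prescribed derives the count from treatment duration and then calls it the number of days of study drug, which implies that they are the same. If so, case 3 gives 63 × 125 = 7,875 mg, and 7,875/175 = 45 mg/day as written against 7,875/84 = 93.75 mg/day with own dates. RDI is then 36% against 75% if the planned daily dose is 125 mg, or 48% against 100% if it is the cycle average of 93.75 mg. The SAP does not say which applies.

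**The case against.** The best defence is that the rest of SAP 6.6.2 points to drug-specific dates. The governing clause is per drug, the duration formulas differ by drug, and the palbociclib offset makes sense only after palbociclib's own last dose. Within such a clause, the phrase could be read as any amount of that drug, as opposed to a missed or interrupted day. A programmer might well have read it so. This stands as evidence of intent. It does not rescue the wording: SAP 6.6.3 uses the phrase for either drug, and no other text supplies the per-drug dates.

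It is also fair to say that the large gaps in cases 3 and 4 come from assumed stop days, that the protocol limits continued on-study palbociclib where it is commercially available and reimbursed, and that the dose-intensity effect depends on an undefined term. Cases 1 and 2 need none of these, only that ZN-c5 is taken into the final rest week.

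A reader might infer that the exposure tables do misreport subjects who could not tolerate a drug, or hide that the drug was stopped. The documents do not support either inference. They do not show how the tables were programmed. SAP 6.6.2 also derives dose modifications, including discontinuation, by reason, and SAP 6.6.3 lists adverse events leading to discontinuation of each drug separately in the Phase 1 combination. Early withdrawal would remain visible there.

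**Conclusion.** Wrong as written, of minor severity. The definition of exposure dates contradicts both the per-drug calculation and the palbociclib offset. On the literal reading, a fully on-schedule subject whose last ZN-c5 dose falls in the rest week has up to 7 days added to palbociclib duration and one whole extra cycle, 21 doses, added to doses prescribed. Where one drug is stopped, the inflation grows with the time for which the other continues; the documents do not give the share of subjects affected or their stop days. The effect on actual daily dose and RDI holds only if days of study drug means treatment duration.

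The reach is narrow: descriptive exposure summaries in combination subjects. That is about 40 in dose escalation, and about 112 more if Combination Phase 2 is run, which the SAP treats as conditional. Monotherapy subjects are unaffected, and CBR, PFS and DLT analyses do not use these durations.

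**What to change.** Replace the definition in SAP 6.6.2 with: dates of exposure for a drug are the dates on which a non-zero dose of that drug is taken. Use these dates in every duration-based formula in the section, and state there whether the number of days of study drug is the treatment duration. If a regimen-level duration is wanted, report it on a separate line under its own name.

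The cost is one phrase and one clarifying sentence. Dosing dates by drug are needed for the per-drug calculation in any case. If the programs already use them, the change only brings the text into line; if not, the combination exposure tables should be rerun.

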- 23. In the Combination Dose Escalation and Combination Phase 2 with palbociclib, the window for the Day 1 visit for subsequent cycles is only + 4 days, since there must always be at least a full 7-day off treatment recovery period for palbociclib before starting the next 21-day dosing cycle.

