6.1.2.2 DOSING AND ADMINISTRATION OF PALBOCICLIB

Palbociclib (IBRANCE®, Pfizer Inc.) at a dose of 125 mg should be taken orally once daily for 21 consecutive days, followed by 7 days off treatment to comprise a complete cycle of 28 days, per the most recent local or US Full Prescribing Information for palbociclib. Subjects should take palbociclib at approximately 24-hour intervals at approximately the same time each day.

On days that PK samples are drawn, palbociclib should be taken with food 2 hours after the ZN-c5 dose.

If a subject vomits or misses a dose, an additional dose should not be taken. The next prescribed dose should be taken at the usual time. Palbociclib should be swallowed whole (do not chew, crush, or open them prior to swallowing). Palbociclib should not be ingested if the medication is broken, cracked, or otherwise not intact.

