8. CHANGES FROM METHODS PLANNED IN THE PROTOCOL

In regard to the Monotherapy Phase 2 Efficacy, section 6.1.7 of the protocol state that efficacy in the Monotherapy Phase 2 will be determined by CBR and results will be combined with those from subjects with similar treatment characteristics (2nd/3rd Line therapy) and treated at the same dose level of ZN-c5 in the Monotherapy Expansion arm. The analysis will simply be done by phase.

An additional population not defined in the protocol, the Tumor Response Evaluable Set has been defined for use in efficacy analyses.

In a Protocol Clarification Letter (15 June 2022), it was announced that study has reached the time point where a data cut-off of 18 May 2022 has been established after the primary objectives of the study have

been met. Beyond this cut-off, only limited information including study drug administration, study drug accountability, and non-serious and serious adverse events were collected in addition to any cases of pregnancy, overdose, or medication error. End of treatment information (reason for discontinuation form only [EOT], not the full visit) and Safety Follow-up information (Date of Visit [DOV] form only, not the full visit) were also collected.

Because this cut-off was adopted by the sites at different dates, subjects who were ongoing may have data reported beyond this cut-off date.

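### SAP 6.6.2 counts palbociclib doses taken and doses prescribed on different days, so the percent of expected doses does not measure adherence

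*SAP*

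**What the plan says.** SAP 6.6.2 derives the exposure parameters separately for each drug. For palbociclib:

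- Treatment duration runs from the last exposure date minus the "first date of exposure + 8 for palbociclib". The added 8 brings in the 7-day rest after the last dose; earlier rest periods already lie inside the span.
- Doses prescribed: "For palbociclib, this will be the ceiling (treatment duration of study drug / 28) * 21".
- Doses taken, by one formula for both drugs: "treatment duration of study drug * planned number of doses per day", minus missed doses.
- Percent of expected doses is taken over prescribed, times 100.
- Total exposure is "the sum of doses taken/administered in mg". Actual daily dose is "total exposure / number of days of study drug". Relative dose intensity (RDI) is actual over planned daily dose.

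Protocol 6.1.2.2 gives palbociclib "once daily for 21 consecutive days, followed by 7 days off treatment". Footnote 23 in Protocol 1.3 says that in the combination parts "the window for the Day 1 visit for subsequent cycles is only + 4 days". Protocol 9.4.4.1 promises the percent of expected doses taken by dose level.

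**The concern.** The denominator has a palbociclib-specific formula that removes rest days. The numerator has none, so it can credit a dose for every rest day. A percentage built this way can exceed 100% for a subject who followed the schedule exactly, and can show 100% for one who missed a third of the doses.

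The rounding up raises a second problem, because any part-cycle is charged as a full block of 21 doses. A short delay or an early stop then changes the denominator by an amount unrelated to the doses that were due. At stake is whether the combination exposure table can be read as the share of scheduled palbociclib doses taken.

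**Working it through.** The documents give no percent-of-doses figure to reproduce, so the formulas are applied directly.

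**Inputs.** Schedule of 21 dosing days in 28 (Protocol 6.1.2.2); later cycles may start up to 4 days late (Protocol 1.3); formulas from SAP 6.6.2.

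**Formulas.** Take k cycles, total start delay d, and the last dose on Day s of the final cycle. On palbociclib's own dates:

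- duration = 28(k − 1) + d + s + 7
- prescribed = ceiling(duration/28) × 21
- taken = duration × planned doses per day − missed

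**Plain reading** (palbociclib's own dates, 1 planned dose per day, rest days and delay days not logged as missed):

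| Case | Duration | Taken / prescribed | Shown | True |
|---|---|---|---|---|
| 1 cycle, full adherence | 28 | 28/21 | 133.3% | 21/21 = 100% |
| 6 cycles, full adherence | 168 | 168/126 | 133.3% | 126/126 = 100% |
| 1 cycle, 3 missed, Day 21 taken | 28 | 25/21 | 119.0% | 18/21 = 85.7% |
| 1 cycle, 7 missed, Day 21 taken | 28 | 21/21 | 100% | 14/21 = 66.7% |
| 2 completed cycles, 1-day delay | 57 | 57/63 | 90.5% | 42/42 = 100% |
| 3 completed cycles, 1-day delay | 85 | 85/84 | 101.2% | 63/63 = 100% |
| 6 completed cycles, 1-day delay | 169 | 169/147 | 115.0% | 126/126 = 100% |
| Stop on Day 10 of Cycle 1, none missed | 17 | 17/21 | 81.0% | 10/10 = 100% |
| 2 cycles, 4-day delay, stop on Day 10 of Cycle 2 | 49 | 49/42 | 116.7% | 31/31 = 100% |

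In the last row the delay does not trigger an extra block. With two cycles and a delay of up to 4 days, it does so only if d exceeds 21 − s.

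**Other readings, full adherence:**

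| Reading | 1 cycle, on schedule | 2 completed cycles, 1-day delay |
|---|---|---|
| Planned doses per day = 21/28 = 0.75 | 28 × 0.75 / 21 = 100% | 57 × 0.75 / 63 = 67.9% |
| 14 rest days (7 per cycle) logged as missed | (28 − 7)/21 = 100% | (57 − 14)/63 = 68.3% |
| Exposure dates are days on which either drug was taken (ZN-c5 to Day 28) | 28 − 1 + 8 = 35; 35/42 = 83.3% | 57 − 1 + 8 = 64; 64/63 = 101.6% |

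**Correcting the numerator alone** leaves the rounding fault. With a 1-day delay, 2 completed cycles give 42/63 = 66.7% and 6 give 126/147 = 85.7%.

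**RDI, one adherent cycle.** Recorded doses sum to 21 × 125 = 2625 mg. Against a planned daily dose of 125 mg, 2625/28/125 = 75% if days means the 28-day duration, and 2625/21/125 = 100% if it means dosing days.

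**The case against.** The strongest objection is that 133.3% is conditional. SAP 6.6.2 does not define planned doses per day or missed doses for palbociclib, and SAP 1 says to read the plan with the eCRFs, which are not available here. With 0.75 planned doses per day, or rest days logged as missed, on-schedule adherence shows exactly 100%. The section also defines exposure dates by any study drug, and taken literally that gives 83.3% for one cycle, the opposite direction. The statement that parameters are calculated separately by drug favours palbociclib's own dates but does not settle the matter. This objection stands: 133.3% belongs to the plain reading and is not a certain output.

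A reader might also infer that the rounding fault always follows a delay and holds whatever is assumed. It does not. A final cycle stopped early may escape the extra block, and an early stop distorts the figure without any delay. On the literal exposure-date reading the extra block is already charged with no delay: 35 days gives 42 prescribed.

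A reader might infer that RDI is wrong as well. The documents show only an undefined term. The ZN-c5 sentence equates days of study drug with treatment duration, but nothing says so for palbociclib.

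Finally, the 85% palbociclib threshold might suggest that DLT evaluability inherits the fault. Protocol 6.1.3 and 8.4.2 and SAP 5.4 state their own Cycle 1 criteria (18 of 21 doses, or 85%) and do not refer to the SAP 6.6.2 percentage.

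**Conclusion.** The rule is wrong as written for palbociclib. Numerator and denominator count different days, and rounding up to whole cycles is a second, separate fault. None of the readings examined gives 100% for full adherence both on schedule and after a permitted 1-day delay. The shown value also changes with the number of cycles once a delay occurs, so no single rescaling repairs it.

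The reach is small. The fault affects descriptive palbociclib exposure tables in the combination cohorts, possibly only the approximately 40 dose-escalation subjects, since SAP 5.2 and SAP 7 treat Combination Phase 2 as conditional. CBR, DLT evaluability and the MTD/RP2D rules are unaffected. It should be corrected because the table would otherwise print either impossible percentages or plausible false ones.

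**What to change.** For palbociclib in SAP 6.6.2:

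1. Use palbociclib's own exposure dates and drop the ceiling.
2. Doses prescribed = scheduled dosing days, that is Days 1–21 of each palbociclib cycle actually started. Count the final cycle to the earlier of Day 21 and the palbociclib stop date or data cut-off.
3. Doses taken = recorded doses, or those scheduled days minus the doses missed on them.
4. State which day count the RDI uses, and define planned daily dose on the same basis: 125 mg over dosing days, or 125 × 21/28 = 93.75 mg over the 28-day cycle. Either pairing gives 100% for one adherent cycle.

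Items 1–3 return 21/21, 18/21 and 14/21 for the single-cycle cases, 42/42 after the 1-day delay and 10/10 for the Day 10 stop.

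The cost is a few formula lines and reprogramming of the palbociclib exposure tables. It depends on palbociclib start, interruption and stop dates being recorded by drug, which cannot be confirmed without the eCRFs. SAP 8 says that after 18 May 2022 "only limited information including study drug administration, study drug accountability, and non-serious and serious adverse events were collected", so the cut-off applied to exposure should be stated. Cycle starts after that date should come from the drug-administration records, because cycle visit dates are not listed among the data still collected. If RDI is put on dosing days, cycle delays need their own summary because that RDI will not show them.

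### The relative dose intensity formula in SAP 6.6.2 has no workable reading for palbociclib: full adherence gives 75%, or dose holds drop out of the calculation

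*SAP*

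**What the plan says.** SAP 6.6.2 says its exposure parameters are calculated separately for each drug, but it gives a single dose-intensity formula for both:

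- Total exposure adds up the mg that the subject actually took.
- For the daily dose actually received, the rule reads: "for ZN-c5 and palbociclib will be calculated as the total exposure / number of days of study drug".
- For RDI, expressed as a percentage, the rule reads: "for ZN-c5 and palbociclib will be calculated as (actual daily dose / planned daily dose) * 100".

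Treatment duration is drug-specific. One rule is "last date of exposure – first date of exposure + 1 for ZN-c5". The other differs only in its constant and its drug: "last date of exposure – first date of exposure + 8 for palbociclib". The constant 8 brings the closing week off into the palbociclib duration.

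The divisor, a count of study-drug days, is not defined, and neither is the planned daily dose. Protocol 9.4.4.1 lists the same day count without defining it. The section offers two hints. The rule for doses prescribed starts from treatment duration and then says: "For ZN-c5, this will be the number of days of study drug for subjects assigned to QD dosing schedule". That treats the day count as duration, but only in the ZN-c5 sentence. The section also defines exposure dates as dates on which drug was taken, which could suggest counting only those days.

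On the schedule, Protocol 6.1.2.2 says palbociclib 125 mg "should be taken orally once daily for 21 consecutive days, followed by 7 days off treatment". The note to Figure 2 in both documents expresses this as 125 mg/day. ZN-c5 is dosed continuously (SAP 3.1).

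**The concern.** RDI should show what share of the intended dose was delivered. For a drug given 21 days in 28, the denominator has to leave out scheduled rest days and keep held or missed dosing days. The SAP makes the rest-week adjustment for palbociclib doses prescribed (21 per 28 days) but not for the actual daily dose or RDI.

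A literal programming of 6.6.2 would therefore produce one of two misleading palbociclib columns. In one, a perfectly taken combination shows a 25-point shortfall. In the other, a subject whose palbociclib was withheld for a whole cycle shows full intensity. Holds and delays are foreseen: Protocol 8.4.3.2 allows non-toxicity palbociclib holds of up to 21 days, and Protocol 8.4.2 makes a delay of more than 7 days to start Cycle 2 a DLT.

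**Working it through.** The documents state no RDI value, so there is no plan figure to reproduce. The check applies the 6.6.2 formulas to test subjects.

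**Inputs.** Palbociclib 125 mg/day, 21 days on and 7 off (Protocol 6.1.2.2; Figure 2 note). Palbociclib duration = last − first + 8; ZN-c5 duration = last − first + 1; RDI = 100 × (total mg / day count) / planned daily dose (SAP 6.6.2). The cycle average 125 × 21/28 = 93.75 mg is an assumption used as a sensitivity case; the documents do not state it.

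**ZN-c5, day count = duration.** With a 21-day hold inside 84 days and no reduction, RDI = 63/84 = 75%, which is what was delivered.

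**Palbociclib, day count = duration.**
- Full adherence over n on-schedule cycles: the last dose falls on day 28(n − 1) + 21, so duration = 28(n − 1) + 21 − 1 + 8 = 28n. RDI = (21n × 125 / 28n) / 125 = 21/28 = 75% for every n. Against 93.75 mg it is 100%.
- Adherent until stopping on day 10 of cycle 1: duration = 10 − 1 + 8 = 17; total = 1,250 mg; actual daily dose = 1,250/17 = 73.5 mg. RDI = 58.8% against 125 mg and 78.4% against 93.75 mg. The true value is 100%.

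**Palbociclib, day count = days taken.**
- Full adherence for one cycle: 2,625/21 = 125 mg. RDI = 100% against 125 mg and 133.3% against 93.75 mg.
- Cycle 2 of 3 withheld: 42 doses on 42 days, so RDI = (42 × 125 / 42) / 125 = 100%. Delivered: 42/63 = 66.7%.
- A 7-day hold inside one 21-day block: RDI = 100%. Delivered: 14/21 = 66.7%.

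| Palbociclib reading | Full cycles, adherent | Adherent, stops day 10 | Cycle 2 of 3 withheld |
|---|---|---|---|
| Duration, 125 mg | 75% | 58.8% | 42/84 = 50% |
| Duration, 93.75 mg | 100% | 78.4% | 50 × 125/93.75 = 66.7% |
| Days taken, 125 mg | 100% | 100% | 100% |
| Days taken, 93.75 mg | 133.3% | 133.3% | 133.3% |
| Correct value | 100% | 100% | 66.7% |

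No row matches the last line in all three columns.

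**The case against.** The strongest reply is that this is an undefined term, not a failed formula. If the planned daily dose means the cycle average, the duration reading is right for palbociclib over complete cycles and for ZN-c5. That is true as far as it goes. However, the documents give no daily palbociclib figure except 125 mg, and the average still fails an adherent subject who stops mid-cycle.

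A reader might also infer that RDI fails for ZN-c5, because counting only days taken would turn the 21-day hold in 84 days into 100%. The documents do not support that. The ZN-c5 sentence in 6.6.2 uses the day count as treatment duration, which keeps held days in the denominator.

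Nor would interruptions vanish from the report. SAP 6.6.2 tabulates dose modifications, including interruptions, by type and reason and counts them. SAP 6.6.3 summarizes adverse events leading to interruption or modification, separately by drug for the Phase 1 combination. Protocol 9.4.4.1 asks for number and timing. Dose reductions still lower RDI under every reading. What those tables do not show is how much dose was lost. The percent of expected doses is not a dependable substitute: duration times one planned dose per day, with no missed doses, gives 28 taken against 21 prescribed, or 133.3%, for an adherent palbociclib cycle.

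Finally, RDI is not an endpoint and is not in the protocol's exposure list. No decision rule uses it. This stands, and it limits the importance of the point.

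**Conclusion.** The point holds for palbociclib. On the readings the text supports, RDI is either 75% for a fully adherent subject or insensitive to every hold. The 75% assumes a planned daily dose of 125 mg. The 100% for a withheld cycle assumes no dose reduction. The ZN-c5 RDI is correct on the SAP's own usage and needs only an explicit statement.

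The reach is limited to descriptive exposure tables, mainly palbociclib in the combination parts. The combination escalation plans about 40 subjects (SAP 3.5.1), and SAP 5.2 treats execution of the combination Phase 2 as conditional. DLTs and DLT evaluability have their own criteria, and CBR does not use RDI. A correction is worthwhile because the printed percentage would be wrong, but it would change no efficacy or dose-finding conclusion.

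**What to change.** For ZN-c5, state that the day count is the treatment duration, last − first + 1.

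For palbociclib, define RDI = 100 × total mg taken / (125 mg × scheduled dosing days). Count scheduled dosing days on a fixed 28-day calendar that starts at the first palbociclib dose and runs to the last. With D = last − first + 1, scheduled days = 21 × floor(D/28) + min(D mod 28, 21).

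- Full adherence, n cycles: D = 28(n − 1) + 21, scheduled 21n, RDI 100%.
- Adherent stop on day 10: 10/10 = 100%.
- Cycle 2 of 3 withheld: D = 77, scheduled 42 + 21 = 63, RDI 42/63 = 66.7%.
- Cycle 2 of 2 started 14 days late: D = 63, scheduled 42 + 7 = 49, RDI 42/49 = 85.7%.

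Counting only Days 1–21 of each started cycle would be simpler, but the last example would then read 42/42 = 100%, and it would be unclear whether a wholly withheld cycle had started.

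The cost is SAP wording and one derivation from dosing dates already collected. Two limits should be stated:

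- Start delays lower RDI only once they add up to more than 7 days, because shorter ones fall in the calendar's last rest week. One 4-day delay in two cycles gives D = 53, scheduled 21 + 21 = 42, RDI 100%. If every later cycle used the full +4-day window, three cycles would give D = 77 + 8 = 85, scheduled 63 + 1 = 64, RDI 63/64 = 98.4%. Six cycles would give D = 161 + 20 = 181, scheduled 126 + 13 = 139, RDI 126/139 = 90.6%.
- A hold that runs straight into discontinuation is not counted for either drug, since both spans end at the last dose.
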